We will design a single blinded randomized trial to study the effects of IVF on benign headaches. There are numerous challenges using the International Headache Society guidelines for controlled drug trials in acute migraines, including having a patient population that knows the specifics of migraine headaches and meets the exact definition. In order to facilitate obtaining the necessary number of patients we will include all benign headache patients [17,18].

METHODS

Study Design

This will be a single center, prospective, single blinded randomized controlled trial on a convenience sample of patients presenting to the adult or pediatric ED with a chief complaint of headache. Subjects will only be enrolled when a physician or research assistant who is familiar with the study protocol is available to enroll patients.

Selection of Participants

Previous data have found that patients presenting to the ED with an undifferentiated headache improve with all the above-described headache medications regardless of whether or not they meet the definition of migraine, tension headache, or another primary headache disorder [7, 8, 11]. Therefore, this study will enroll all patients between the ages of 10 and 65 who meet all of the inclusion criteria and do not meet any of the exclusion criteria, who present to the ED with a benign headache.

Inclusion Criteria

Patients who present to the ED with complaint of a headache with the following criteria:

- Age 10 to 65 years
- Temperature < 100.4° F
- Normal neurologic exam and normal mental status

Exclusion Criteria

- Pregnant.
- Meningeal signs are present
- Acute angle closure glaucoma is suspected.
- Head trauma within the previous two weeks
- Lumbar puncture within the previous two weeks
- Thunderclap onset of the headache
- Known allergy to one of the study drugs.
- History of intracranial hypertension.
- Is a prisoner
- Patient declined informed consent
- Non-English speaking patient or parent/guardian for pediatric patients
- Attending provider excludes patient
- Severe dehydration

Informed Consent

Written, informed consent will be obtained from each patient. Consent will include a discussion of the risks and benefits. In addition to parental informed consent in the pediatric population, age appropriate verbal assent will be obtained from pediatric subjects.

Risk/Benefit

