The risks are the side effects associated with each drug. For prochlorperazine, this includes drowsiness, blurred vision, xerostomia, congestion, nausea, akathisia, tardive dyskinesia, NMS, and blood dyscrasias. For Benadryl include sedation, tiredness, sleepiness, dizziness, constipation, dry mouth, blurred vision, nausea, and loss of appetite. For normal saline, this

includes injection site swelling, redness, infection, venous thrombosis or phlebitis or hypervolemia. Personal benefits include intended reduction in headache symptoms and the satisfaction that the patient may be assisting investigators in determining a more effective headache treatment.

Interventions

After enrollment, each patient will be randomized either to the standard treatment arm to receive prochlorperazine 0.15 mg/kg up to 10 mg IV along with diphenhydramine 1mg/kg (up to 50 mg) IV and normal saline at 5 mL/h IV OR to the study arm to receive prochlorperazine along with diphenhydramine IV and normal saline at 20 mL/kg (up to 1000 mL) given IV over 1 hour. The diphenhydramine will be administered first, and immediately afterward the prochlorperazine will be administered. The patient will then be connected to normal saline on an IV pump and randomized to 5 cc over an hour or 20 cc/kg (maximum 1000 cc) over one hour. The IV bag and pump will be covered so that the patient will not know how much fluid they are receiving. Patients will undergo simple randomization to either the fluid bolus group or the control group. The treating physician will consult a folder that contains a list specifying the group assignment. Each row of the list corresponded to a patient, and will be covered by a small slip of opaque paper that will be removed at the time of enrolment to reveal the group assignment. This list was constructed at the beginning of the study using a random number generator by a research staff. Randomization in the pediatric ED and adult ED will be separate to ensure equal numbers of pediatric patients in both the experimental and control arms (blocking). Emergency providers will be instructed not to administer any rescue medications for at least 30 minutes.

Safety

After 30 minutes, the treating provider will be permitted to administer a “rescue medication” of their choice for further treatment. If there is an untoward event that requires the patient to know which IVF dose was administered, patient will unblinded and will not continue in the study.

Reportable Events

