Anticipated side effects are those listed on the manufacturer’s package insert and are treated as routine non-urgent or non-emergent events are not reportable events.

Adverse Events are those unanticipated side effects that require interventions or anticipated side effects that do not respond to intervention.

Serious Adverse Events are those side effects that require Advanced Life Support measures to control symptoms.

AEs and SAEs will be reported to the IRB within 5 days of the event.

Methods of Measurement

Enrolled patients will fill out a brief data collection form to include age, sex, race, phone number, and baseline headache severity using a 100-mm visual analog scale (VAS). Repeat headache severity scores will be measured at 30 and 60 minutes. Time zero begins immediately after complete administration of the study drug. Nausea (with a 100 mm VAS) and vomiting will also be assessed at these time intervals. The need for rescue medications will be extracted from the patient's chart at a later time.

Trained research assistants will call the patient 24-48 hours post-discharge by phone to ask if they are currently having a headache (yes or no) and to rate their current pain (0-10). If the patient is admitted, the patient will be approached in the hospital by an investigator or research assistant for follow up.

Outcome Measures

The primary outcome measure will be the difference in pain scores between the 5 cc over an hour and 20 mg/kg (up to 1000 cc) over an hour groups measured as the absolute difference between the means at 60 min. Secondarily, we will measure the difference between the rates of decline in pain scores, rate of admission, nausea scores, rate of vomiting, rate of use of additional medications for headache, and headache resolution with telephone follow up.

Privacy and Security

In order to protect the privacy of the research subjects and to maintain the confidentiality of data, all data will be managed only by trained research assistants or investigators and will be stored in the locked Emergency Medicine research offices and electronic data will be stored on a password protected computer in the locked Emergency Medicine research office. All research assistants and investigators are HIPAA- trained, CITI trained and credentialed by UMC IRB, and oriented to the study protocol.

Data Analysis:

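### Use of additional headache medication is a chart record of what a provider who has been shown the arm chose to give, so it cannot be read as patient need; one question to the masked patient would help

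*Combined protocol and SAP*

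**What the plan says.** The Study Design section describes a "single center, prospective, single blinded randomized controlled trial on a convenience sample". Under Interventions, the masking is of the patient: "The IV bag and pump will be covered so that the patient will not know how much fluid they are receiving". The treating physician is not masked: "The treating physician will consult a folder that contains a list specifying the group assignment". The slip over each row "will be removed at the time of enrolment to reveal the group assignment".

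Under Safety, after a 30-minute wait, "the treating provider will be permitted to administer a “rescue medication” of their choice for further treatment". No pain threshold, patient request or masked decision-maker is attached to that permission.

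Under Methods of Measurement, "The need for rescue medications will be extracted from the" patient's chart. In the ED the patient gives a headache VAS (baseline, 30 and 60 minutes), a nausea VAS and vomiting status. At 24 to 48 hours the patient reports headache yes/no and pain from 0 to 10. No item asks whether the patient wants more treatment.

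Under Outcome Measures, the secondary outcomes include "rate of admission, nausea scores, rate of vomiting, rate of use of additional medications for headache". The Data Analysis section names no test for medication use or admission.

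**The concern.** An outcome meant to show whether patients needed more treatment should come from the patient, from a masked assessor, or from a rule applied alike in both arms. Here it comes from a free choice by someone who may know the arm.

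The Introduction calls IV fluid a common part of headache treatment in the ED. A provider who knows that a patient is receiving 5 mL over the hour could therefore feel that usual care is being withheld and give another drug at a pain level that would not prompt one in the bolus arm. A provider who considers a litre sufficient could hold back. Either lean would make fluid appear to reduce rescue use when only prescribing differed. Fuller chart extraction cannot remove this, because the chart faithfully records the decision and the decision is where the bias enters.

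What is at stake is the reading of a stated secondary outcome that could influence practice.

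**Working it through.** **Step 1. Who knows what, and who decides.**

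| Question | Answer in the protocol | Section |
|---|---|---|
| Who is masked? | The patient (covered bag and pump) | Interventions |
| Who sees the arm, and when? | The treating physician, at enrolment, before any outcome is measured | Interventions |
| Who decides on rescue? | The treating provider, by choice, once 30 minutes have passed | Safety |
| How is rescue recorded? | Extracted from the chart later | Methods of Measurement |
| Is the patient asked about wanting more treatment? | No | Methods of Measurement |
| Who decides admission, and on what criteria? | Not stated | none |

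The protocol uses both treating physician and treating provider. I read them as the same person or the same care team; nothing suggests that a second, masked clinician makes the rescue decision.

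**Step 2. The plan's own figure.** With SD 22 mm, difference 13 mm, two-sided alpha 0.05 and 80% power:

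n per arm = 2 × (1.960 + 0.842)² × 22² / 13² = 44.96, rounded up to 45.

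The stated 45 reproduces. It concerns the 60-minute pain score, and this point does not disturb it.

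**Step 3. What a provider lean could do.** The protocol gives no rescue rate and no measure of provider lean, so both are assumed. Suppose need is identical in the two arms, but knowledge of the arm moves medication use apart by a gap g, split evenly around an average rate p. The rates are then p + g/2 and p − g/2. With 45 per arm, I enumerated every pair of binomial counts (x, y) and summed the probability of those with |z| > 1.96, where

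z = (x − y)/45 ÷ √[2 p̂(1 − p̂)/45], with p̂ = (x + y)/90.

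The Yates version reduces |x − y|/45 by 1/45 before dividing. For scale, at p = 30% the standard error of the difference is √(2 × 0.30 × 0.70 / 45) = 9.7 percentage points.

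Probability of a significant difference with equal need:

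| Average rate | Test | No gap | 5 points | 10 points | 15 points |
|---|---|---|---|---|---|
| 20% | uncorrected | 5.4% | 9.7% | 23.0% | 44.8% |
| 20% | Yates | 2.5% | 5.1% | 14.4% | 32.5% |
| 30% | uncorrected | 5.3% | 8.6% | 18.6% | 35.4% |
| 30% | Yates | 2.9% | 5.1% | 12.5% | 26.4% |
| 40% | uncorrected | 4.9% | 7.5% | 15.8% | 30.2% |
| 40% | Yates | 2.7% | 4.6% | 10.7% | 22.4% |

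If the lean only raises one arm from 30%, the uncorrected figures are 8.4%, 17.4% and 31.5%.

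The Yates rows are shown because chi-squared with that correction is the only categorical test the protocol names, and it names it for baseline severity. No calculation is offered for admission.

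**The case against.** The strongest reply is that single blinding is declared, the primary outcome is a pain score from the masked patient, and the outcome list calls the measure a rate of use, which is accurate for chart data; the word need appears only in the measurement sentence. Masked symptom measures (headache VAS, nausea VAS, follow-up headache status) already stand beside the chart outcomes. The illustrated error rates rest on assumed rates, an assumed lean and a test the protocol does not plan. With Yates correction, a 5-point lean stays near the nominal 5%.

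Most of this stands, and it limits the weight of the point. It does not remove it. Declaring a single-blind design does not make a provider's decision readable as patient need, and the protocol carries no caution on this.

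A reader might go further in four ways that the documents do not support:

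- **That provider belief will bias the result.** The protocol leaves this possible but gives no rate or lean from which to judge it.
- **That admission is equally established as an unmasked provider's choice.** No decision-maker is named. Attributing it to the treating provider is an inference from ordinary ED practice, and a question about wanting medicine does nothing for it.
- **That a composite of wanting more medicine or having already received it would cure the problem.** It would put the provider's decisions between 30 and 60 minutes back into the outcome.
- **That someone else could readily uncover the assignment.** The protocol does not say who sets the pump, so feasibility is not shown.

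**Conclusion.** The point holds for use of additional headache medication. As planned, a difference between arms would mix patient need with the beliefs of a provider who has been shown the arm, and chart data cannot separate the two. For admission the same caution is probable rather than shown.

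The size is unknown. Across assumed average rates of 20% to 40%, a 10-point provider-driven gap would produce a false significant difference in about 16% to 23% of trials uncorrected, or 11% to 14% with Yates correction. These figures assume 45 per arm, equal need, a gap split around the average and a test at the two-sided 5% level that the protocol does not specify. They show what a lean of that size would do, not that one exists.

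The sample size is unaffected. Because the pain score is the masked patient's own, this point is not a criticism of how the primary outcome is ascertained; whether rescue given before 60 minutes alters that score is a separate matter. I class this as a cheap improvement.

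**What to change.** 1. In Methods of Measurement, add one yes/no question to the masked patient straight after the 60-minute VAS: whether more headache medicine is wanted now. Asking it after the score leaves the primary measurement untouched.
2. In Outcome Measures, add that answer as a patient-reported secondary outcome in its own right, not combined with medication given.
3. Because rescue is allowed from 30 minutes, also show the answer split by whether rescue had already been given. State that the answer can still be affected by earlier provider-decided rescue, so the item lessens the problem without removing it.
4. Keep chart-recorded medication use and admission, but describe them as care decisions made with knowledge of the arm (for admission, adding that the decision-maker is not specified). Do not interpret either as evidence of patient need or of fluid efficacy. Replace the word need in the sentence on chart extraction.

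The cost is one item at an existing contact and a few revised sentences. The question may prompt some patients to request treatment after the primary measurement, and two chart outcomes will be reported more cautiously. No change is proposed to when or which rescue may be given, or to who handles the assignment slip.

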Assuming a SD of 22 (based on prior data from our institution), we calculated that we would need 45 patients in each group to find a clinically important difference in pain score reduction (13 mm) between groups at 60 min with at least 80% power and an alpha of 0.05.

The groups will be compared using a t -test on gender, race, and age; and a chi (with Yates correction)-squared test on severity of presenting headache, to determine if they are similar. The individual VAS measurements will be compared using a repeated measures analysis of variance (ANOVA) test.

REFERENCES

[1] R.B. Lipton, M.E. Bigal, M. Diamond, F. Freitag, M.L. Reed, W.F. Stewart, et al. Migraine prevalence, disease burden, and the need for preventive therapy. *Neurology*, 68 (2007), pp. 343–349

[2] B.W. Friedman, J. West, D.R. Vinson, M.T. Minen, A. Restivo, E.J. Gallagher. Current management of migraine in US emergency departments: an analysis of the National Hospital Ambulatory Medical Care Survey. *Cephalalgia*, 35 (2015), pp. 301–309

[8] Jones J, et al. Randomized double-blind trial of intravenous prochlorperazine for the treatment of acute headache. *JAMA*. 1989;261:1174-1176.

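### Two planned baseline tests do not fit their variables: a t-test on race, and a Yates-corrected chi-squared test on presenting severity, described only as a 100-mm VAS with no stated cut (minor; baseline table only)

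*Combined protocol and SAP*

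**What the plan says.** The baseline comparison is one sentence in Data Analysis. The arms are to be compared "using a t -test on gender, race, and age; and a chi (with Yates correction)-squared test on severity of presenting headache". The second part of the sentence ends with the purpose: "a chi (with Yates correction)-squared test on severity of presenting headache, to determine if they are similar".

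Methods of Measurement says how these variables are collected: "Enrolled patients will fill out a brief data collection form to include age, sex, race, phone number", together with "baseline headache severity using a 100-mm visual analog scale (VAS" (the quotation stops inside the bracket). No race categories or codes are given, and no cut or grouping for presenting severity appears anywhere. The only other pain scale is the 0-10 rating at telephone follow-up, which is not a measure of presenting severity.

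Elsewhere the plan treats the VAS as continuous. Outcome Measures uses a difference in means at 60 minutes, the sample size uses an SD of 22, and Data Analysis states: "The individual VAS measurements will be compared using a repeated measures analysis of variance (ANOVA) test".

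Under Interventions, allocation is described as follows: "Patients will undergo simple randomization to either the fluid bolus group or the control group". The pediatric and adult departments are randomized separately.

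**The concern.** A t-test compares means. Age has a mean, and a two-level variable coded 0/1 has one too (a proportion), but nominal race does not. With three or more categories, the analyst must give each one a number, and the p-value then depends on an ordering that carries no meaning.

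For severity the mismatch runs the other way. A measurement in millimetres is assigned a test for a 2x2 table. That test needs a two-group split, and the documents state none.

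What is at stake is the baseline table and any statement drawn from it that the arms are alike. A non-significant test is weak support for such a statement in any case, and weaker still if the p-value reflects a coding order or comes from a conservative test on a split scale.

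**Working it through.** **1. The plan's own figure.** Inputs from Data Analysis: SD 22, difference 13 mm, alpha 0.05 (two-sided assumed), power 80%.

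n = 2 × 22² × (1.960 + 0.842)² / 13² = 44.96, so 45 per group, as stated. With the t distribution, SE = 22 × √(2/45) = 4.638, noncentrality = 13/4.638 = 2.803 on 88 df, and power = 0.792. None of the baseline tests enters this calculation.

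**2. Race, illustrative table.** The documents give no race data. Assume 45 per arm in categories A/B/C with counts 22/8/15 against 15/18/12. Each code order and its reverse give the same p-value, so there are three distinct results:

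| Codes for A, B, C | Arm means | t | p |
|---|---|---|---|
| 1, 2, 3 | 1.844 vs 1.933 | −0.50 | 0.619 |
| 1, 3, 2 | 1.689 vs 2.067 | −2.20 | 0.031 |
| 2, 1, 3 | 2.156 vs 1.867 | 1.80 | 0.076 |

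Pearson chi-squared needs no codes. The expected counts are 18.5, 13 and 13.5 in each arm, giving a statistic of 5.50 on 2 df and p = 0.064.

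**3. Race, null simulation.** 40,000 trials, 45 per arm, the same assumed category shares in both arms.

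- Any single code order rejects in 4.7% to 5.4% of trials, so the error rate of one fixed coding is about right.
- With three categories, the verdict differs between code orders in 11% to 13% of trials.
- With two levels, the t-test and the uncorrected chi-squared test disagree in at most 0.4% of trials.

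**4. Gender and age.** Age is continuous, so the t-test suits it. For gender, an illustrative 30/45 against 22/45 gives p = 0.090 by t-test and 0.088 by uncorrected chi-squared. That is nearly harmless.

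**5. Severity, null simulation.** Assumed: normal VAS, mean 70, SD 20 or 22, 45 per arm, no true difference, 40,000 trials.

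- The t-test rejects in about 5% of trials.
- The Yates-corrected test rejects in 2% to 3% at cuts of 50, 60, 70, 80 and 90 mm.
- The Yates verdict differs between cuts of 50, 60, 70 and 80 in about 8% of trials.

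To show the lost information, assume a true 13 mm imbalance with SD 22. The t-test detects it in 79% of simulations, and a Yates test split at the midpoint in 51%.

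**6. Separate calculation for the optional covariate** (it does not measure this error). Start from power 0.792 and let r be the assumed correlation between baseline and 60-minute VAS. Adjustment multiplies the SE by √(1 − r²) relative to unadjusted 60-minute means, or by √((1 + r)/2) relative to change scores. Each row takes SD 22 as the SD of its own unadjusted endpoint, because the plan does not say which it is.

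| Compared with | r = 0.3 | r = 0.5 | r = 0.7 |
|---|---|---|---|
| Unadjusted 60-minute means | 83% | 89% | 97% |
| Change scores | 93% | 89% | 85% |

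The second row falls as r rises, because change scores already capture more of the gain when the correlation is high.

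**The case against.** The strongest reply is that almost nothing depends on these tests. They trigger no action, and a trial would use one race coding, which rejects at about the nominal rate. All of that stands, and it is why the point is minor. A reader might take the 11% to 13% as an inflated false-positive rate. It is not: it counts disagreement between alternative codings, and nothing in the documents suggests that several would be tried. The 8% for severity likewise compares hypothetical cuts.

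Second, the data collection form is not in the documents. Race might be recorded in two levels, and a severity cut might be defined there. This also stands. A reader might infer that the severity test cannot be run, or that a cut would be chosen after seeing the data. The documents support only that no cut is stated.

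Third, the sentence may be a drafting slip with the two tests exchanged. That is possible, but a clean exchange would put chi-squared on age, which the present text handles correctly. The sentence needs editing either way.

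Fourth, dropping baseline significance tests altogether is a general preference. It would apply equally to well-chosen tests, so it is not part of this error.

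**Conclusion.** The point holds as a minor one, confined to the baseline table. The mismatch follows from the text alone: a nominal variable is assigned a comparison of means, and a scale in millimetres is assigned a 2x2 test with no stated cut. For race, it matters only if there are three or more categories, a number the plan does not give. For severity, the cost is lost information and a conservative test.

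The sizes rest on assumed race counts and shares, and on an assumed VAS mean and SD, since the documents supply none of these. A reader might infer that the trial's main result is compromised. The documents do not support that: the primary outcome is the difference in means at 60 minutes, and neither it nor the sample size uses these tests.

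**What to change.** Rewrite the one sentence so that each method fits its variable: chi-squared or Fisher's exact test, or simply n and %, for sex and race; a t-test or rank test, or simply mean and SD, for age and baseline VAS. If a grouped severity comparison is wanted, state the cut in advance. The cost is one sentence, with no change to data collection, sample size or patient burden.

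A separate and optional improvement, which does not repair this error, is to pre-specify the baseline VAS as a covariate in the 60-minute comparison. It is already collected, so the cost is one more sentence. The possible gain is shown in the last step of the working. The gain over the planned repeated measures ANOVA is not quantified, because the plan does not say whether baseline is one of the measurements in that model.

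### The plan does not say how, or whether, baseline pain enters the 60-minute comparison, and it judges baseline balance by a significance test that cannot show similarity

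*Combined protocol and SAP*

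**What the plan says.** Methods of Measurement has each enrolled patient record "baseline headache severity using a 100-mm visual analog scale (VAS"), with repeat scores at 30 and 60 minutes. Outcome Measures defines the primary outcome as the difference in pain scores between arms, "measured as the absolute difference between the means at 60 min". That definition has no baseline term. A secondary outcome there is how fast pain falls in each arm.

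Data Analysis contains three relevant statements:
- The sample size is set to find a "clinically important difference in pain score reduction (13 mm) between groups at 60 min".
- The arms are compared on presenting severity by a Yates-corrected chi-squared "test on severity of presenting headache, to determine if they are similar".
- One sentence covers how pain scores are analysed: "The individual VAS measurements will be compared using a repeated measures analysis of variance (ANOVA) test".

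No covariate, ANCOVA or adjusted estimate appears anywhere. The ANOVA sentence does not say whether baseline is one of the time points or which contrast gives the 60-minute result. Under Interventions, randomization is simple, with the pediatric and adult EDs randomized separately. It is not stratified by pain severity.

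**The concern.** There are two linked problems.

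First, under randomization any baseline difference between arms is chance, so a hypothesis test of it answers no useful question. A non-significant result does not show that the arms are similar, because with 45 per arm the test misses sizeable gaps. The plan also does not say what follows from a significant result, which leaves room to decide on adjustment after seeing the data.

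Second, baseline pain is likely to predict pain at 60 minutes. If it is left out of the primary comparison, or enters only as a subtraction, the standard error is larger than it needs to be. The text allows at least three analyses: raw 60-minute means, change from baseline, or some term of a repeated-measures ANOVA. These can differ materially in power, so the choice should be fixed in advance.

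**Working it through.** **Inputs from Data Analysis.** SD 22 mm ("Assuming a SD of 22 (based on prior data from our institution"), difference 13 mm, "we would need 45 patients in each group", "with at least 80% power and an alpha of 0.05". Sidedness is not stated; two-sided reproduces the plan's number.

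**Assumptions, not in the documents.** The correlation r between baseline and 60-minute VAS is shown over a range. Variance is taken as equal at the two times. Baseline SD is taken as 22 mm for the similarity check.

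**1. The plan's own figure.** n per arm = 2 × 22² × (1.960 + 0.842)² / 13² = 44.96, so 45. This reproduces, with power 80.0% by the normal approximation. The noncentral t distribution with 88 df gives 79.2%, and would need 46 per arm. The t-based figures are used below.

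**2. What the similarity test can show.**
- SE of the baseline difference = 22 × √(2/45) = 4.64 mm, so chance alone gives a 95% range of about ±9.1 mm.
- An observed gap of 8 mm gives t = 8/4.64 = 1.72 and p = 0.088, which would pass as similar. A gap of 8 mm or more arises by chance in about 8% of such trials: 2 × (1 − Φ(1.725)) = 0.085.
- A t-test on the full VAS has 19% power for a true 5 mm difference and 57% for 10 mm.

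These figures are for a t-test. The plan names a chi-squared test and gives no severity categories, so its own test cannot be evaluated exactly. It is unlikely to detect imbalance better.

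**3. Power for 13 mm at 45 per arm, if SD 22 is that of the 60-minute score.** ANCOVA residual SD = 22√(1 − r²), 87 df. Change-score SD = 22√(2(1 − r)), 88 df.

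| r | Unadjusted 60-min score | Change score | ANCOVA |
|---|---|---|---|
| 0.2 | 79% | 59% | 81% |
| 0.3 | 79% | 65% | 83% |
| 0.4 | 79% | 72% | 86% |
| 0.5 | 79% | 79% | 89% |
| 0.7 | 79% | 95% | 97% |

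**4. Power for 13 mm at 45 per arm, if SD 22 is that of the change.** ANCOVA residual SD = 22√((1 + r)/2).

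| r | Change score | ANCOVA |
|---|---|---|
| 0.3 | 79% | 93% |
| 0.5 | 79% | 89% |
| 0.7 | 79% | 85% |

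**5. Can the repeated-measures ANOVA fill the gap?** If baseline is one of its time points, the baseline-to-60-minute part of the group-by-time term is the change score. Its variance factor 2(1 − r) exceeds the ANCOVA factor 1 − r² by (1 − r)², so it is never smaller. The group main effect would average in a pre-treatment score that treatment cannot affect. If baseline is not a time point, the ANOVA makes no use of it.

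**The case against.** The strongest reply is that the plan does use baseline. The repeat scores follow a baseline score on the same scale, so a natural reading makes baseline one of the ANOVA's repeated measurements. The sample-size sentence speaks of reduction, and a secondary outcome concerns the rate of decline. This stands as far as it goes. A reader might infer that baseline pain is used nowhere except in the similarity test, or that any analysis without ANCOVA wastes it. The documents support neither: a change score uses baseline, and at r = 0.7 it is far better than the raw 60-minute score (95% against 79% when SD 22 is that of the 60-minute score). What remains is that the plan does not specify how baseline enters, and that the routes it hints at are no more precise than ANCOVA.

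A reader might also infer that an imbalance passed as similar biases the result. It does not. The unadjusted comparison is unbiased under randomization, and chance imbalance is already part of its standard error. At r = 0.5 an 8 mm gap would move the raw 60-minute difference by 8 × 0.5 = 4 mm, but that shift and the wider standard error are the same loss described twice.

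Nor is the sample size wrong: 45 per arm follows from the plan's inputs. It is also fair to say that no stated decision depends on the similarity test, and that the gain is small if r is low (about two points at r = 0.2).

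**Conclusion.** The point holds as one of precision and pre-specification. The plan collects baseline VAS, writes its primary outcome without it, names no covariate, and leaves open how the ANOVA uses it. Its test of presenting severity cannot establish similarity.

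The size depends on r, which the documents do not give, and on which SD the 22 describes. Under the first reading, ANCOVA raises power from 79% for the unadjusted score to between 81% and 89% for r from 0.2 to 0.5. Under the second, it raises power from 79% for the change score to between 93% and 85% for r from 0.3 to 0.7. ANCOVA gains under both readings, assuming equal variances at the two times. Because t-based power at 45 per arm lies just below the stated 80%, even a small gain is useful. The change should be made, but the trial is valid without it.

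**What to change.** In Data Analysis:

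1. Remove the baseline significance tests and their stated purpose. Present baseline characteristics, including VAS, descriptively by arm.
2. Pre-specify the primary result as the adjusted mean difference in 60-minute VAS with 95% CI, from ANCOVA with baseline VAS as covariate and ED (pediatric or adult) as a factor, because randomization is separate by ED. An equivalent choice is the 60-minute contrast of a repeated-measures model of the 30- and 60-minute scores with the same two terms. State that this model is used whatever imbalance is seen, and align the repeated-measures sentence with it.
3. State whether SD 22 is that of the 60-minute score or of the change.

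This takes a few sentences and needs no new data and no more patients. The statistical cost is one degree of freedom for baseline VAS and one for ED.
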